3 STUDY IMPLEMENTATION

3.1 STUDY DESIGN

This trial is unique in that it is intended to establish the rationale and conditions for the use of oral DAC-THU and pembrolizumab therapy for NSCLC, EsC, and MPM. The goal is to establish the basis for subsequent evaluation of this treatment regimen in combination with other agents targeting MDSC, or adoptive immunotherapy regimens in patients with thoracic malignancies.

Patients potentially eligible for trial will be evaluated, and undergo subsequent eligibility assessment in the Thoracic Surgery Clinic/NCI. Patients meeting eligibility criteria will undergo baseline (if fresh tumor biopsy was not performed at screening) and post treatment tumor biopsies either by percutaneous image-guided FNA techniques in Interventional Radiology (Clinical Center/NIH) or endoscopic/thoracoscopic techniques in the CC operating room by Thoracic Surgery staff using standard of care practice guidelines. Tumor biopsies may be omitted at the discretion of the PI if risks outweigh potential research benefits.

The Phase I component will be a standard 3+3 design starting with oral DAC-THU on two consecutive days (preferably Tuesday and Wednesday) for two weeks out of three weeks for 9

weeks with incremental dose escalation as shown in Section **3.1.3**. Patients with high PD-L1 tumor expression will be combined with patients with low PD-L1 tumor expression to minimize accrual numbers required for the Phase I component of the study. Pembrolizumab will be administered on Wednesday, Thursday or Friday at a fixed intravenous dose of 200 mg q 3 weeks. One cycle is three weeks; one course is 9 weeks. Treatment evaluation including repeat tumor biopsy will be performed after one course of therapy (Week 10 +/- one week). Those patients exhibiting disease progression or unacceptable toxicities will be removed from study. Patients exhibiting stable disease or disease regression will be offered an additional course of therapy followed by treatment evaluation (without mandatory biopsy). Treatment will continue in this manner until off-study criteria have been met.

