3.1.2 Definition of Dose Limiting Toxicity (DLT)

DLT is defined as:

- Any Grade 3 or greater toxicity that cannot be attributed to a cause other than study treatment during the first two cycles of Course 1 of DAC-THU and/or pembrolizumab therapy such as disease progression or intercurrent illness.
- Any toxicity that cannot be attributed to a cause other than study treatment (DAC-THU and/or Pembrolizumab) that results in study treatment discontinuation.

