3.1.3 Dose Escalation

The revised dosing regimen selected for this trial is based on pharmacodynamic evidence of systemic hypomethylation without significant systemic toxicities mediated by oral DAC-THU in patients with sickle cell disease in a recent Phase 1 clinical trial (108), as well as experience with DAC-THU/Pembrolizumab in NSCLC (Section 1.2.11.2). The frequency of DAC-THU dosing will increase using a conventional 3+3 Phase I study design attempting to maximize systemic DNMT1 depletion while avoiding Grade 3 or greater systemic toxicities (primarily neutropenia/thrombocytopenia). *Due to the uncertainty regarding cumulative toxicities, no intrapatient escalation will be allowed.*

Dose escalation will proceed as indicated in **Table 7** using three patients per dose level (irrespective of Tumor PD-L1 expression) until DLT within the first 6 weeks (two cycles) of DAC-THU therapy is observed. If one of three patients at any given dose level experiences DLT, up to three additional patients will be treated at this dose level. If only one of six patients exhibit DLT, subsequent patients will be enrolled into the next higher dose level. As soon as two patients at any given dose level develop DLT, no additional patients will be entered at that level. Subsequent patients will be accrued into the preceding dose level; if DLT is observed in less than two of six patients treated at this lower level, this dose will represent maximum tolerated dose (MTD).

Table 7: DAC-THU Dosing Schema for High (50% or Greater) and Low (0-49%) PD-L1
Expression Groups

Dose Level	DAC	DAC	THU	THU	Frequency^
	mg/kg/course	mg/kg/day*	mg/kg/course	mg/kg/day*	wk 1,2,4,5,7,8
-1	2.0	0.17	120	10	T;W
1	2.5	0.21	120	10	T;W
2	3.0	0.25	120	10	T;W
*on days a	administered				
^ T: Tuesd	lay; W: Wednesday				

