3.3 DOSING DELAYS AND MODIFICATIONS

This study is intended to evaluate the safety and potential efficacy of oral DAC-THU and pembrolizumab as epigenetic immunotherapy in patients with NSCLC, EsC and MPM. The proposed oral DAC dose of ~0.17 mg/kg to be combined with THU ~10 mg/kg administered 60 minutes before oral DAC, is based on non-human primate studies and the Phase 1 clinical trial in SCD which had an identical pharmacologic objective of DAC distribution through tissues with high CDA expression (intestines, liver etc.), and the wide concentration-time profile desired for non-cytotoxic DNMT1-depletion. This dose of DAC administered orally is 10-20% of the FDA-approved dosages administered intravenously and is < 50% of the dose of oral decitabine administered together with another CDA-inhibitor (a THU-analogue) in clinical trials by Astex/Otsuka.

Although it is anticipated that this therapy will be well tolerated at the revised doses, myelosuppression resulting from reprogramming of hematopoietic stem cell differentiation may become dose limiting (50). If dose limiting myelosuppression is observed during the first 2 cycles of Course 1, DAC-THU will be held until toxicities have resolved to Grade 2 or less, and DAC-THU therapy will recommence at the next lower dose, or at the SAME dose if deemed appropriate by the PI, as indicated in the dose escalation schema (**Table 7**). Only one dose reduction will be allowed.

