3.3.5 Dose Modification of DAC-THU

Table 9 lists standard laboratory values that should trigger dose modifications of the investigational drug.

General Adverse Events	Action		
Non-hematological, Grade 1 or 2 (excluding hemorrhage)	 Continue DAC-THU therapy at full dose prescribed. Apply maximum supportive care recommendations. If prolonged duration of Grade 2 adverse event (≥ 7 days) is affecting quality of life, start the next treatment cycle at DL-1. If event persists and continues to affect quality of life for ≥ 7 more days following initial dose reduction, discontinue DAC-THU. 		
Grade 3 ALT and AST	 Hold DAC-THU therapy until recovery to Grade ≤ 1. If ALT and AST resolve to Grade ≤ 1 within 10 days, maintain current dose level. If ALT and AST do NOT resolve to Grade ≤ 1 within 10 days, dose reduce 1 level. If Grade 3 ALT or AST occurs after dose reduction, discontinue DAC-THU. 		

 Table 9: Trigger Values that Result in Dose Modification

General Adverse Events	Action	
Grade 4 ALT and AST	 Hold DAC-THU therapy until recovery to Grade ≤ 1. Resume DAC-THU at DL-1. If Grade 4 toxicities occur after dose reduction, discontinue DAC-THU. 	
Non-hematological, Grade 3 or 4 (excluding ALT, AST, hemorrhage and QT prolongation)	 Apply maximum supportive care recommendations. Hold DAC-THU until recovery to Grade ≤ 1 and resume DAC-THU at the next lower dose level. If symptoms continue to persist at Grade 3 or 4, following dose reduction, discontinue drug. 	
QT prolongation, Grade 3 or 4	 Cardiology consultation will be obtained to determine whether any cardiac functional assessment is warranted or if therapy should be delayed or discontinued. When warranted, ECGs will subsequently be reviewed by the NCI consulting cardiologist. If therapy is continued, dose reduce 1 level for Grade 4 events. If Grade 3 or 4 toxicities occur after dose reduction discontinue DAC-THU. 	
Thrombocytosis	 If platelet count > 500/ mcL but < 1.2M/mcL, continue DAC-THU at current dose. Begin ASA 325mg PO daily. If platelet count 1.2M /mcL or more, hold DAC-THU until platelet count < 1.2 M/mcL, begin ASA 325 mg PO daily and resume DAC-THU at DL-1 if within the first two Cycles of Course 1; or at SAME dose or DL-1 per PI discretion in subsequent cycles. 	
Hemoglobin	• Hgb > 18 g/dL: hold DAC-THU until Hgb WNL. Resume DAC-THU at DL-1.	
Hematological Adverse Events		

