6.3.2 Definitions

Evaluable for toxicity: All patients will be evaluable for toxicity from the time of their first treatment with DAC/THU/pembrolizumab. Dose limiting toxicities will be assessed during the first 3 weeks of DAC-THU/pembrolizumab therapy.

Evaluable for objective response: Patients who have measurable disease present at baseline, have received at least 9 weeks of DAC-THU/pembrolizumab therapy (one full course), and have had their disease re-evaluated will be considered evaluable for response provided: (1) the patient demonstrates progressive disease or death while on protocol therapy; (2) the tumor is not removed surgically prior to the time complete response or partial response is confirmed; or (3) the patient demonstrates a complete or partial response as confirmed according to protocol criteria. These patients will have their response classified according to the definitions stated below. [Note: Patients who electively terminate therapy before completing 9 weeks of DAC-THU/pembrolizumab therapy and do not expire within 14 days from start of treatment will be replaced. Patients who experience disease progression after 3 weeks of drug therapy but before

completing the minimum of 9 weeks of drug therapy will be taken off-treatment and will only be evaluable for toxicity (not evaluable for response)].

Evaluable Non-Target Disease Response: Patients who have lesions present at baseline that are evaluable but do not meet the definitions of measurable disease, have received at least 8 weeks of DAC-THU/pembrolizumab therapy, and have had their disease re-evaluated will be considered evaluable for non-target disease. The response assessment is based on the presence, absence, or unequivocal progression of the lesions.

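### Section 6.3.2 assesses DLTs for 3 weeks, but the DLT definition (3.1.2) and the escalation rule (3.1.3) use two cycles, which is 6 weeks

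*Combined protocol and SAP*

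**What the plan says.** The combined protocol and SAP gives a period for counting DLTs in three places.

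- **3.1.2, first criterion:** Grade 3 or greater toxicity that cannot be put down to another cause counts if it occurs "during the first two cycles of Course 1 of DAC-THU and/or pembrolizumab therapy".
- **3.1.3:** three patients are treated per dose level "until DLT within the first 6 weeks (two cycles) of DAC-THU therapy is observed".
- **6.3.2, under evaluability for toxicity:** "Dose limiting toxicities will be assessed during the first 3 weeks of DAC-THU/pembrolizumab therapy".

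Section 3.1 fixes the units: "One cycle is three weeks; one course is 9 weeks". Two further places are consistent with two cycles. Section 3.3 sets out what to do "If dose limiting myelosuppression is observed during the first 2 cycles of Course 1", and the thrombocytosis row of Table 9 says to "resume DAC-THU at DL-1 if within the first two Cycles of Course 1", with different handling afterwards.

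**The concern.** The MTD is a Phase I primary objective (1.1.1), and Cohorts 2 to 5 are all treated at it (2.3.1). The 3+3 rule turns on single events: one DLT in six lets a level pass, and two close it. A Grade 3 event in weeks 4-6 that cannot be attributed to anything but treatment is a DLT under 3.1.2 and 3.1.3, yet falls outside the assessment period in 6.3.2.

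Section 6.3.2 is headed as definitions, and its sentence on evaluability for toxicity is a natural place for an analyst or data manager to look. Someone who took the period from there would leave the whole second cycle out of the count that sets the Phase II dose.

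**Working it through.** **Inputs**

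- Cycle length: 3 weeks (3.1).
- DAC-THU: 2 days a week in weeks 1, 2, 4, 5, 7 and 8 (Table 7).
- Pembrolizumab: every 3 weeks (3.1, 3.2.2).
- Escalation rule (3.1.3): one DLT in three patients adds up to three more; one in six allows the next level; two at a level close it; fewer than two of six at the preceding level makes that level the MTD.

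**Step 1. Reproduce the stated period.** 2 cycles x 3 weeks = 6 weeks, which matches 3.1.3. The period in 6.3.2 is 3 weeks = 1 cycle, and 3/6 = one half.

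**Step 2. Side by side.**

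| Place | Period | Weeks |
|---|---|---|
| 3.1.2, first criterion | first two cycles of Course 1 | 6 |
| 3.1.3, escalation rule | two cycles | 6 |
| 3.3, dose-limiting myelosuppression | first two cycles of Course 1 | 6 |
| Table 9, thrombocytosis and Grade 3 hematological rows | first two cycles | 6 |
| 6.3.2 | 3 weeks | 3 |

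The rows for 3.3 and Table 9 govern dose modification, not DLT counting, but they mark off the same period. Only 6.3.2 differs.

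**Step 3. Treatment covered by each window.**

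- Check on the schedule: THU 120 mg/kg per course / 10 mg/kg per day = 12 dosing days, and 6 weeks x 2 days = 12.
- Weeks 1-3 (dosing in weeks 1 and 2): 2 x 2 = 4 DAC-THU days.
- Weeks 1-6 (dosing in weeks 1, 2, 4 and 5): 4 x 2 = 8 DAC-THU days.
- The 3-week window therefore covers 4 of 8 DAC-THU days, and one of the two pembrolizumab infusions (cycle 1 but not cycle 2).

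**Step 4. Direction.** Every patient with a DLT in weeks 1-3 also has one in weeks 1-6. For any given set of patients, the 3-week count is therefore at most the 6-week count. Using 6.3.2 can make a level look safer, never less safe.

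**Step 5. A case where the decision changes.** One of the first three patients has a DLT in week 2, so three more are enrolled under either window. One of those three has a Grade 3 DLT in week 5 and stays on treatment.

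- Count under 3.1.2 and 3.1.3: 1 + 1 = 2 of 6. The level closes.
- Count under 6.3.2: 1 + 0 = 1 of 6. The level passes. At level 1 that means escalation. At level 2, the top level in Table 7, it means the level is not closed.

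**The case against.** The strongest reply is that the intended window is not in doubt. Section 3.1.2 is the DLT definition, and 3.1.3 is the only place that states the escalation and MTD rules; it gives the period both in weeks and in cycles. Against these, 6.3.2 is one line within the response criteria, and an attentive team would probably apply 6 weeks. Nor would events in weeks 4-6 be missed. Laboratory tests are twice weekly in Course 1 (3.4.2), adverse events are assessed weekly during dose finding (Appendix 3), the team reviews prior patients' toxicity before deciding on dose levels (7.4.1), and four more patients are treated at the MTD (3.1). This stands as a limit on the harm. It does not remove the contradiction: the question is which events count, and no text reconciles the two periods.

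Three stronger readings are tempting, and the documents do not support them.

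- **A third, unlimited window.** A reader might infer this from the second DLT criterion in 3.1.2, "Any toxicity that cannot be attributed to a cause other than study treatment (DAC-THU and/or Pembrolizumab) that results in study treatment discontinuation", which states no period. But 3.1.3 can be read as limiting any DLT, including these, to 6 weeks for escalation. An open-ended criterion could also be deliberate, and limiting it would be the less cautious choice.
- **A protocol argument for a longer window.** Section 3.1.3 says "Due to the uncertainty regarding cumulative toxicities, no intrapatient escalation will be allowed". That explains the ban on raising the dose within a patient. It says nothing about how long DLTs should be observed.
- **A probability of a wrong decision.** The chance that a level clears is (1-q)^3 + 3q(1-q)^2 x (1-q)^3, where q is the DLT rate. This is 0.71 at q = 0.20 and 0.91 at q = 0.10. If the six-week rate were 20% and half of those DLTs first appeared in weeks 4-6, the two windows would differ by 0.20. Over assumed rates of 10% to 30% and late shares of 25% to 50%, the gap runs from 0.04 to 0.32. Neither input is in the readable text; Section 1.2.11.2, which 3.1.3 cites for experience with the combination, was not available. The figures also suppose that the team follows 6.3.2 over the 3+3 section's own rule. They are not estimates of risk in this trial.

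**Conclusion.** Wrong as written. The period in 6.3.2 contradicts 3.1.2 and 3.1.3 and is half as long, and 6.3.2 is the text to correct. What is established is the factor of two, the loss of 4 of 8 DAC-THU dosing days and one of two infusions from the window, the one-way effect on the count, and the existence of cases where 2/6 becomes 1/6. None of this depends on an assumed DLT rate. How often a decision would change is not established. Practical harm is limited, because the toxicity data for weeks 4-6 will exist and the escalation section states the right period. The correction is still worth making, because one event can settle a dose level and the MTD is the dose for every Phase II cohort.

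The second criterion of 3.1.2 is a separate matter. Whether toxicity discontinuations after week 6 should count toward the MTD is for the protocol team to decide.

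**What to change.** In 6.3.2, replace the 3-week period in the DLT sentence with: *the first two cycles (6 weeks) of Course 1*. All the timed statements on DLTs then agree (2 x 3 = 6 weeks). The cost is one wording edit in an amendment. It adds no patients, visits or tests, because the scheduled laboratory work and adverse event assessments already cover weeks 4-6. No change to the second criterion of 3.1.2 is included in this fix.

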3.1.1 Study Schema

Treatment evaluation including staging studies and biopsy will be performed on Days 64 and 65 +/- 7 days. DAC-THU will be given on two consecutive days as indicated, with Tuesday/Wednesday optimal but not absolute. Pembrolizumab may be administered on Wednesday, Thursday, or Friday for administrative convenience.

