6.3.5 Response Criteria for Radiographic Studies

6.3.5.1 Measuring of Soft Tissue Disease

a. Evaluation of Target Lesions

Complete Response (CR)

Disappearance of all target lesions. Any pathological lymph nodes (whether target or non-target) must have reduction in short axis to < 10 mm.

Partial Response (PR)

At least a 30% decrease in the sum of the diameters of target lesions, taking as reference the baseline sum diameters.

Progressive Disease (PD)

At least a 20% increase in the sum of the diameters of target lesions, taking as reference the smallest sum on study (this includes the baseline sum if that is the smallest on study). In addition to the relative increase of 20%, the sum must also demonstrate an absolute increase of at least 5 mm. (Note: the appearance of one or more new lesions is also considered progressions).

Note: For this study, determination of PD will not be made prior to the Day 60 evaluation.

Stable Disease (SD)

Neither sufficient shrinkage to qualify for PR nor sufficient increase to qualify for PD, taking as reference the smallest sum diameters while on study.

b. Evaluation of Non-Target Lesions

Complete Response (CR)

Disappearance of all non-target lesions and normalization of tumor marker level. All lymph nodes must be non-pathological in size (< 10 mm short axis).

Note: Tumor markers alone cannot be used to assess response. If tumor markers are initially above the upper normal limit, they must normalize for a patient to be considered in complete clinical response.

Non-CR/Non-PD (Stable Disease, SD)

Persistence of one or more non-target lesion(s) and/or maintenance of tumor marker level above the normal limits.

Progressive Disease (PD)

Appearance of one or more new lesions and/or *unequivocal progression* of existing nontarget lesions. *Unequivocal progression* should not normally trump target lesion status. It must be representative of overall disease status change, not a single lesion increase.

Although a clear progression of "non-target" lesions only is exceptional, the opinion of the treating physician should prevail in such circumstances, and the progression status should be confirmed at a later time by the review panel (or Principal Investigator).

c. Evaluation of Best Overall Response

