The best overall response is the best response recorded from the start of the treatment until disease progression/recurrence (taking as reference for progressive disease the smallest measurements recorded since the treatment started). The patient's best response assignment will depend on the achievement of both measurement and confirmation criteria.

Target Lesions	Non- Target Lesions	New Lesions	Overall Response	Best Overall Response when Confirmation is Required*
CR	CR	No	CR	\geq 4 wks. Confirmation**
CR	Non-CR Non-PD	No	PR	\geq 4 wks. Confirmation**
CR	Not evaluated	No	PR	
PR	Non- CR Non-PD Not evaluated	No	PR	
SD	Non- CR Non-PD Not evaluated	No	SD	Documented at least once \geq 4 wks. from baseline**
PD	Any	Yes or No	PD	
Any	PD***	Yes or No	PD	No prior SD, PR or CR
Any	Any	Yes	PD	

For Patients with Measurable Disease (i.e., Target Disease)

* See RECIST 1.1 manuscript for further details on what is evidence of a new lesion.

** Only for non-randomized trials with response as primary endpoint.

*** In exceptional circumstances, unequivocal progression in non-target lesions may be accepted as disease progression.

- d. Patients with a global deterioration of health status requiring discontinuation of treatment without objective evidence of disease progression at that time should be reported as "*symptomatic deterioration*." Every effort should be made to document the objective progression even after discontinuation of treatment.
- e. In some circumstances, it may be difficult to distinguish residual disease from normal tissue. When the evaluation of complete response depends on this determination, it is recommended that the residual lesions be investigated (fine needle aspirate/biopsy) before confirming the complete response status.

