Since published data have demonstrated a response rate of 45% for first-line pembrolizumab alone in NSCLC patients with PD-L1 expression of 50% or greater (95), (98), this trial will try to demonstrate if a response rate in excess of 45% may be realized in NSCLC patients with \geq 50% PD-L1 expression by the addition of DAC/THU. Briefly, NSCLC patients with high intratumoral (50% or greater) PD-L1 expression will be evaluated for response as part of a Simon optimal twostage Phase II trial design (116) in order to rule out an unacceptably low PR+CR rate of 35% (p0=0.35) in favor of an improved response rate of 60% (p1=0.60). With alpha=0.10 (probability of accepting a poor treatment=0.10) and beta=0.20 (probability of rejecting a good treatment=0.20), the first stage will determine the response rate in 10 evaluable patients, including those NSCLC patients among the 10 who are treated at the MTD from the Phase I cohort who have high intra-tumoral PD-L1 expression. If 0 to 4 of the 10 patients have a clinical response, then no further patients will be accrued. If 5 or more of these 10 patients have a response, then accrual would continue until a total of 23 evaluable patients have been treated at the MTD. As it may take up to several months to determine if a patient has experienced a response, a temporary pause in the accrual may be necessary to ensure that enrollment to the second stage is warranted. If there are 5 to 10 patients with a response out of 23 patients, this would be an uninterestingly low response rate. If there were 11 or more of 23 (47.8%) who experienced a response, this would be sufficiently interesting to warrant further study in later trials. Under the null hypothesis (35% response rate), the probability of early termination is 75.2%.

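### Patients who progress between week 3 and week 9 are declared not evaluable for response, so both Simon cohorts drop known treatment failures and the response rate is biased upward

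*Combined protocol and SAP*

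**What the plan says.** Section 6.3.2 makes a patient evaluable for objective response only after at least 9 weeks of therapy (one full course) and a re-evaluation of disease, provided one of three conditions holds. Condition (1) is that "the patient demonstrates progressive disease or death while on protocol therapy". A bracketed note follows. Patients who stop electively before 9 weeks and "do not expire within 14 days from start of treatment will be replaced". Patients who progress after 3 weeks but ahead of "completing the minimum of 9 weeks of drug therapy will be taken off-treatment and will only be evaluable for toxicity (not evaluable for response").

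Section 10 counts both Simon designs in evaluable patients. For the high PD-L1 cohort, "accrual would continue until a total of 23 evaluable patients have been treated at the MTD"; the low PD-L1 cohort goes from 10 to 29 in the same way. Section 10.1 defines the response rate as a percentage of patients with a best response of CR or PR and does not name the denominator. No all-treated response analysis is specified.

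Three other places bear on who is excluded:

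- Section 6.3.5.1: "For this study, determination of PD will not be made prior to the Day 60 evaluation".
- Section 3.1.1: "Treatment evaluation including staging studies and biopsy will be performed on Days 64 and 65 +/- 7 days".
- Section 6.3.5.1, item d: "Patients with a global deterioration of health status requiring discontinuation of treatment without objective evidence of disease progression" are to be reported as symptomatic deterioration.

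**The concern.** Early progression is a treatment failure. Removing a patient from the denominator because of that failure can only raise the observed response rate. Since accrual runs to a fixed number of evaluable patients, the excluded patients are in effect replaced. This is an inference, because the note in 6.3.2 speaks of replacement only for elective stoppers.

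Condition (1) does not bring these patients back. It applies to patients who already meet the 9-week requirement, and the note then excludes early progressors outright.

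The stage 1 and final decisions in both NSCLC cohorts rest on this count. For the high PD-L1 cohort, Section 10 says "this trial will try to demonstrate if a response rate in excess of 45% may be realized", and a rate among completers flatters the regimen in that comparison. The 2-of-10 rules for EsC and MPM are affected only if inevaluable patients there are replaced beyond 10. The total of 78 evaluable patients in Section 10 suggests this, but the wording that up to 10 will be accrued does not state it.

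**Working it through.** **Inputs (Section 10).** High PD-L1: p0 = 0.35, p1 = 0.60; stop at 4 or fewer of 10; success at 11 or more of 23; alpha 0.10, beta 0.20; early termination under p0 75.2%. Low PD-L1: p0 = 0.10, p1 = 0.30; stop at 1 or fewer of 10; success at 6 or more of 29; alpha 0.05, beta 0.20; early termination 73.6%.

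**The plan's own figures.** With stage 1 size n1 and stopping bound r1, total n and final bound r, and response probability q:

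- Early termination = P(X1 ≤ r1), X1 ~ Bin(n1, q).
- P(success) = Σ over x from r1+1 to n1 of P(X1 = x) · P(X2 ≥ r+1−x), X2 ~ Bin(n−n1, q).

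High cohort: early termination 0.7515, type I error 0.0977, power 0.804. Low cohort: 0.7361, 0.0471, 0.805. Both designs reproduce, so the Simon arithmetic is sound. The fault is in the population it is applied to.

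**Effect of the exclusion.** Let f be the fraction of treated patients excluded. If all are non-responders, the response rate among evaluable patients is the all-treated rate divided by (1−f). With the all-treated rate at p0, the rules are evaluated at q = 0.35/(1−f) and 0.10/(1−f):

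| f | q, high / low | Type I error, high / low | Early termination, high / low |
|---|---|---|---|
| 0 | 0.350 / 0.100 | 0.098 / 0.047 | 0.752 / 0.736 |
| 5% | 0.368 / 0.105 | 0.132 / 0.058 | 0.710 / 0.716 |
| 8.9% | 0.384 / 0.110 | 0.165 / 0.068 | 0.673 / 0.698 |
| 10% | 0.389 / 0.111 | 0.177 / 0.071 | 0.661 / 0.693 |

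If only half of those excluded are progressors and the other half (for example elective stoppers) respond like the remaining patients, then q = p0/(1−f/2). Type I error is then 0.113 / 0.052 at f = 5% and 0.132 / 0.058 at f = 10%.

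**Where the range for f comes from.** The documents give no value. The accrual ceiling shows what the plan could absorb:

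- Spare places: 85 − 78 = 7. Response-evaluable patients with every cohort filled: 23 + 29 + 10 + 10 = 72. So f = 7/(72+7) = 8.9%.
- With replacement in the Simon cohorts only, f = 10% needs 23/0.9 → 26 and 29/0.9 → 33. Adding 20 EsC and MPM patients and 6 Phase I patients not at the MTD gives 26 + 33 + 20 + 6 = 85.

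**At the success boundary (high cohort).** 11/23 = 47.8%; with one excluded progressor 11/24 = 45.8%; with two, 11/25 = 44.0%.

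**Whether the Day 60 rule empties the excluded group.** The first evaluation can fall from Day 64 − 7 = 57 to Day 65 + 7 = 72. In the Section 3.1 calendar, week 9 is Days 56–62. A scan on Days 60–62 can therefore record progression before the ninth week ends, depending on how the 9 weeks are counted. Section 3.3.1.1 also requires no evidence of progression on Day 1 of each cycle, and Section 3.6.1 removes progressors from therapy; both can act inside the exclusion window. Patients who stop early for symptomatic deterioration also fail the 9-week condition, and the note does not say how they count.

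**The case against.** The strongest reply is that the excluded group may be very small.

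- Progression is not called before the Day 60 evaluation.
- Week 9 is free of scheduled drug: DAC-THU is given in weeks 1, 2, 4, 5, 7 and 8, and the third pembrolizumab infusion falls in week 7. A patient scanned on Days 60–62 has had every dose of the course and could be read as having completed it.
- Section 6.3.3.4 asks for confirmation of progression at the next restaging unless clinically not indicated, which takes patients past week 9.

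At f = 1–2%, type I error is only 0.104–0.110 (high) and 0.049–0.051 (low). The 8.9% describes spare places for any kind of inevaluability and is not evidence about progressors. If p0 was meant for evaluable patients, alpha is as stated. The 44.0% example needs two exclusions at exactly 11 responses, and 45% is not the tested null. Counting elective stoppers as non-responders is also a choice of estimand.

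Much of this stands as a limit on size. It does not remove the defect. The per-cycle progression check and the removal rule leave a route to early progression, and confirmed progression is dated back to first detection. If the Day 60 rule did empty the group, 6.3.2 and 6.3.5.1 would contradict each other and still need correction. Reading p0 as a rate among completers keeps alpha nominal, but the result then no longer describes all treated patients. Early elective stoppers are not known failures; they add bias only so far as they would not have responded.

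**Conclusion.** The concern holds: the definition is wrong as written and must be fixed. Followed literally, it drops known failures from the primary endpoint in both Simon cohorts, and the direction of the bias does not depend on f.

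The size does depend on f, which is an assumption and probably small. It is slight at 1–2%. At 5% both error rates exceed their stated limits, clearly in the high cohort and modestly in the low one. These error rates assume that p0 refers to all treated patients, that excluded patients do not respond, and that they are replaced. Confidence in the reading of the text is high; the magnitude is a range.

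**What to change.** In 6.3.2 and 10.1, define the primary response population, for the Simon rules and the 2-of-10 rules, as all patients with measurable disease who received at least one dose at the MTD. Count anyone without a confirmed CR or PR as a non-responder, whether from early progression, early stop, symptomatic deterioration, death or no scan. Replace only patients who never start treatment. Delete the clause that makes early progressors not evaluable for response, and keep the 9-week completers as a supportive analysis. State that p0 and p1 refer to all treated patients. Reconcile the 6.3.2 note with its own condition (1), the Day 60 rule in 6.3.5.1 and the Day 57–72 evaluation window in 3.1.1.

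This is a change of definition with no new procedures and fewer replacement patients. The reported response rate will be somewhat lower. If p1 was meant for completers, power at the unchanged boundaries, evaluated at 0.60(1−f) and 0.30(1−f), falls from 0.80 / 0.81 (high / low) to 0.73 / 0.77 at f = 5%, 0.67 / 0.73 at 8.9% and 0.65 / 0.72 at 10%. Restating p0 and p1 may then mean revisiting the boundaries and sample sizes.
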